This study conducted a randomized encouragement trial to encourage use of the existing mail order pharmacy among diabetes patients with poor adherence to CVD risk factor medications who use only retail pharmacies. Subjects were randomized to (2) arms: 1) the intervention arm and 2) the usual care arm. Those randomized to the intervention arm, at all sites, received encouragement to use mail order pharmacy services by receiving an outreach letter, which includes information about the benefits of mail order pharmacy use, and information on how to enroll in mail order pharmacy services at their individual site. In addition, those randomized to the encouragement at KPNC and KPHI received an encouragement outreach email (secure message) and a pre-recorded phone message. Since phone and email contact with patients is not standard of care with HPHC, they received letter-only encouragement outreach. There was no outreach follow-up. Observational EHR data was used to examine the impact of the intervention on mail order use and medication adherence. Those patients randomized to the usual care arm did not receive any form of encouragement outreach from the study team.

STUDY POPULATION:

a. NUMBER OF SUBJECTS

63,012 total participants

b. INCLUSION AND EXCLUSION CRITERIA

Inclusion Criteria:

- Age 18 years or older
- Have a diagnosis of diabetes as indicated by EHR
- Have active health plan membership in the past 12 months
- Non-adherent (PDC <80%) to at least one oral CVD risk factor medications in the past 12 months
- Have no evidence of mail order pharmacy use to refill oral CVD risk factor medications.

Exclusion Criteria:

- Pregnancy or Dementia/Traumatic Brain Injury diagnosis in the past 12 months
- Hospitalized, in Skilled Nursing Facility, Hospice, or Home Health at the time of randomization

WAIVER OF INFORMED CONSENT and HIPPA PRIVACY RULE AUTHORIZATION:

A waiver of informed consent and HIPPA Privacy Rule Authorization was granted from KPNC IRB (IRB of record for this study) for participants in the study intervention. The only known risk is disclosure of confidential information. Safeguards were be put in place to prevent the loss of privacy and to prevent breaches of confidentiality. This study represented no more than minimal risk participants.

STUDY PROCEDURES:

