To examine the relationship of encouraging MOP use with MOP use and adherence, we estimated the differences in MOP use and CVD medication adherence at follow-up between the two arms using Chi-square tests in an intent-to-treat (ITT) analysis. Differences in the percentages of CVD drug fills delivered by mail were estimated using T-Test. To determine whether MOP use differed by race/ethnicity we calculated risk ratios using modified Poisson regression comparing the effect of treatment on outcomes within each group. We used Chi-square tests to compare the percent of patients with a hospitalization or emergency department visit during follow-up between the intervention and control arm and compared the number of primary care visits between arms using the Kruskal-Wallis test. Patients who died or who disenrolled from their health plan during follow-up were excluded from the analysis. In addition, those who did not have a CVD medication fill during the follow-up period were also excluded since we were unable to assess whether they used MOP. Sensitivity analysis was conducted to assess the impact of those without CVD medication fills during follow-up by including them in the analytic population as non-users of MOP at follow-up. All analyses were further stratified by site and results from both the KP sites were collapsed based on the similarity of study results in the two sites, and because their pharmacy distribution structure and health care systems were also similar in comparison to HPHC.

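### The comparison labelled intent-to-treat drops patients who die or disenrol after randomisation and never restores them, so it is a modified ITT analysis of stayers with a fill

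*Combined protocol and SAP*

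**What the plan says.** The study design section of the protocol describes a two-arm randomised trial: "Subjects were randomized to (2) arms: 1) the intervention arm and 2) the usual care arm". The DATA ANALYSIS section compares MOP use and CVD medication adherence at follow-up "between the two arms using Chi-square tests in an intent-to-treat (ITT) analysis".

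The same section then removes two groups defined by what happened after randomisation:

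- Deaths and disenrolments: "Patients who died or who disenrolled from their health plan during follow-up were excluded from the analysis". No reason is given.
- No-fill patients: "those who did not have a CVD medication fill during the follow-up period were also excluded". The reason given is that their use of MOP could not be determined.

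One sensitivity analysis is described: "Sensitivity analysis was conducted to assess the impact of those without CVD medication fills during follow-up". It works "by including them in the analytic population as non-users of MOP at follow-up". It mentions neither deaths nor disenrolments and sets no rule for adherence.

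The exclusion sentence names no outcome, so it appears to cover the hospitalisation, emergency department and primary care comparisons as well.

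**The concern.** An intent-to-treat label tells the reader that everyone randomised is compared in the arm assigned. Here, membership of the analysed set depends on staying alive, staying enrolled and filling a CVD prescription, all of which are settled after randomisation. The plan checks the effect of one of these exclusions on the primary outcome (no fill) and leaves the others unchecked.

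Two things are at stake:

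- **A false difference.** If the outreach changed who disenrols, or how many, the arms would no longer be comparable among those analysed. Disenrolment is the more plausible route; a letter, email or recorded call about mail order is unlikely to alter mortality.
- **The target population.** Even with identical exits in both arms, the estimate is the effect among stayers with a fill, not the effect of offering outreach to all randomised patients.

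The plan describes no count of exits by arm, and no censoring, weighting, imputation or bounding for leavers. A reader therefore cannot judge either point.

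**Working it through.** **Text check.** The label is ITT, death and disenrolment are exclusions, and the only restoration is of no-fill patients for MOP use. Could the no-fill sensitivity analysis also bring back patients who left without a fill? The section introduces the no-fill patients as a further group, separate from deaths and disenrolments, so the text does not support that reading.

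**Inputs for size.** The documents give "63,012 total participants". They do not say whether this count is before or after exclusions, and they give no allocation ratio, exit rate, MOP rate, adherence rate or follow-up length. There is no plan figure to reproduce. Everything below is illustrative. It assumes 1:1 allocation, so 63,012 / 2 = 31,506 per arm.

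**1. Equal and alike exits.** Let a share f leave in each arm.

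Effect in all randomised = (1-f) × effect in stayers + f × effect in leavers.

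If leavers show no response, the ratio of the stayers' effect to the all-randomised effect is 1/(1-f):

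- f = 0.05: 1/0.95 = 1.05
- f = 0.10: 1/0.90 = 1.11
- f = 0.15: 1/0.85 = 1.18

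If leavers respond somewhat, but less than stayers, the ratio lies between 1 and these values. With no true effect in either group the difference is 0, so no false positive arises.

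**2. Unequal exits, MOP use, no true effect.** Assume 10% use among all randomised in both arms and no use among leavers. A share d exits in usual care and d - δ in the intervention arm. The spurious difference is 0.10/(1-d+δ) - 0.10/(1-d). It is negative here because the arm that keeps more non-users shows the lower rate; reversing the imbalance reverses the sign.

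| d | δ | Spurious difference (points) | Two-sided type I error |
|---|---|---|---|
| 5% | 1 point | -0.11 | 7.2% |
| 10% | 1 point | -0.12 | 7.5% |
| 15% | 1 point | -0.14 | 7.8% |
| 5% | 2 points | -0.22 | 14.1% |
| 10% | 2 points | -0.24 | 15.2% |
| 15% | 2 points | -0.27 | 16.6% |

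For scale, 31,506 per arm has 80% power for a difference of about 0.67 points at 10% use.

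**3. Unequal exits, adherence, no true effect.** Assume 48% adherent overall, a share L of leavers adherent, and exit shares f and f + δ. The spurious difference is (0.48 - (f+δ)L)/(1-f-δ) - (0.48 - fL)/(1-f).

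- Low corner (f = 0.05, δ = 0.005, L = 0.40): 0.458/0.945 - 0.460/0.95 = 0.04 points.
- High corner (f = 0.15, δ = 0.02, L = 0.30): 0.429/0.83 - 0.435/0.85 = 0.51 points.

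The standard error of the adherence difference, at 50% adherent, is sqrt(2 × 0.25/31,506) = 0.40 points.

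**4. How unusual would such imbalances be?** By chance alone, the standard error of the between-arm exit difference is sqrt(2 × 0.10 × 0.90/31,506) = 0.24 points at 10% exit, and sqrt(2 × 0.15 × 0.85/31,506) = 0.28 points at 15%. A 2-point imbalance is then about 8 or 7 standard errors. Even 1 point is about 4 at 10% exit. Imbalances of this size would mean that the outreach itself changed retention.

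**The case against.** A reader might infer that the exclusions break the randomisation and that the reported contrasts are biased. The documents do not support that. Bias under no effect needs exits that differ by arm in number or kind, and nothing in the text suggests they do. The letter and email went out once, the recorded call was limited to the two Kaiser Permanente sites, and the subject was a service that already existed. The larger figures in steps 2 and 3 need a causal effect on retention for which there is no evidence. This part of the objection stands.

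It also stands that 1/(1-f) is an upper bound. It assumes that leavers never respond, although their fills before exit may include mail fills. It describes a change of target population, not a false positive. Nor can the adherence figures fairly be set against an expected effect: the 8-point association in the background section is observational and concerns antidiabetic drugs, and the plan gives no expected uptake to multiply it by.

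Scoring patients up to exit has difficulties of its own. Over a short window one fill can cover most of the days, so an 80% PDC threshold does not mean the same as over a full window, and patients with no fill would still need a PDC rule. If retention did differ, so would observation time. Suppose leavers behave like stayers, use is 10% over full follow-up and 5% over half, and exits differ by 2 points: the all-randomised analysis then carries 0.02 × 5 = 0.10 points of difference from retention alone, where the stayers-only analysis carries none. Finally, the section is written as completed work, and exchanging the main and sensitivity analyses afterwards is harder to defend than adding to them.

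These arguments limit the size of the problem and the reach of the remedy. They do not rescue the label or supply the missing analysis.

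**Conclusion.** The point holds as one of labelling, target population and a missing check. The analysis described is not intent-to-treat: it is a modified ITT analysis of patients who stayed alive and enrolled and had a CVD fill. No described analysis restores patients who died or disenrolled, for either outcome.

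The documents do not let a reader tell whether the contrast is biased. With equal and alike exits there is no spurious difference under no effect, and the uptake effect is overstated by at most 5% to 18%. That rests on an assumed 5% to 15% exit and on leavers responding no more than stayers and not adversely. The spurious differences under unequal exits (about 0.1 to 0.3 points for MOP use, 0.04 to 0.51 for adherence) show what could happen. They are not estimates of what did happen.

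**What to change.** 1. Report deaths, disenrolments and no-fill exclusions by arm, and say whether 63,012 is the count before or after them.
2. Add an all-randomised analysis of the primary outcome. Count as use any CVD fill by mail from randomisation to the earliest of end of follow-up, death or disenrolment, and everything else as non-use. No-fill patients are then handled as in the existing sensitivity analysis.
3. Describe the current analysis as modified ITT.
4. For adherence, add a sensitivity analysis and keep the current main analysis. Options are PDC over days alive and enrolled, with a stated rule for patients without a fill, or weighting or bounds for leavers. Worst-case bounds are wide: with a share d excluded in each arm, the full-set difference is (1-d) times the observed one, plus or minus d, so plus or minus 5 to 15 points for d of 5% to 15%.

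The cost is extra analysis and some added text. It assumes that leavers' fills up to exit are held. This is likely, because outcomes come from health records and eligibility already used fill history, but the documents do not say so. MOP rates will fall slightly in both arms, and observation time could differ by arm if retention does, so the exit counts in item 1 should be read alongside the result.

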Encouraging Mail Order Pharmacy Use to Improve Outcomes and Reduce Disparities

NCT02621476

Document date: 10/1/2020

Encouraging Mail Order Pharmacy Use to Improve Outcomes and Reduce Disparities

CLINICAL TRIAL PROTOCOL

Abbreviations:

CVD: cardiovascular disease

HPHC: Harvard Pilgrim Health Care Institute

IVR: automated telephone call (interactive voice response)

KP: Kaiser Permanente

KPNC: Kaiser Permanente Northern California

KPHI: Kaiser Permanente Center for Health Research, Hawaii

LDL: Low-density lipoprotein

PDC: Proportion of Days Covered

OBJECTIVE:

In this study, we seek to determine whether targeted, patient-centered interventions to encourage mail order pharmacy use will result in greater rates of mail order pharmacy use as well as improvements in medication adherence. We conducted a randomized encouragement trial to encourage use of the existing mail order pharmacy among diabetes patients with poor adherence to CVD risk factor medications who use only retail pharmacies and examined whether the intervention's impact differs across key subgroups. The specific aims of this clinical trial are to:

Aim 1: To test whether outreach strategies to encourage mail order pharmacy use will increase rates of mail order pharmacy use (Primary Outcome) in diabetes patients at high risk for poor health outcomes.

Aim 2: To examine whether encouraging the use of mail order pharmacy services to deliver cardiometabolic medications results in greater medication adherence, and to assess differences in the impact of the intervention across key subgroups.

BACKGROUND:

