Eligible patients were randomized into (2) arms: 1) an intervention arm and 2) a usual care arm. Those randomized to the intervention arm, at all sites, received encouragement to use existing mail order pharmacy services by receiving an outreach letter, which includes information about the benefits of mail order pharmacy use, and information on how to enroll in mail order pharmacy services at their individual site. The instructions on how to enroll in the existing mail order pharmacy services came directly from health plan operations materials. In addition, those randomized to the encouragement arm at KPNC and KPHI also received an encouragement outreach email (secure message) and pre-recorded phone message. Since phone and email contact with patients is not standard of care with HPHC, they received letter-only encouragement outreach. The letter and email outreach will be delivered only once. The Interactive Voice Response (IVR) system was programmed to make up to the IRB approved maximum attempts to contact eligible participants via phone to play the approved pre-recorded message: If a call is answered, the message begins. No PHI was disclosed in the outbound message. At the end of the call patients were given the opportunity to be transferred to their local mail order pharmacy phone line. Eligible members can hang up at any time and were not re-dialed. Those patients randomized to the usual care arm did not receive any outreach from the study team.

DATA ANALYSIS:

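### As written, the Aim 2 adherence comparison is called ITT but drops patients with no CVD fill after randomisation, and no described analysis gives them an adherence value

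*Combined protocol and SAP*

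**What the plan says.** Aim 2 (OBJECTIVE) asks whether encouraging mail order services "to deliver cardiometabolic medications results in greater medication adherence". DATA ANALYSIS covers MOP use and CVD medication adherence in a single sentence and compares the arms "using Chi-square tests in an intent-to-treat (ITT) analysis", so the label applies to both outcomes.

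The same section then lists three exclusions, each decided by what happens during follow-up. First, "Patients who died or who disenrolled from their health plan during follow-up were excluded from the analysis". Then, patients that "did not have a CVD medication fill during the follow-up period were also excluded since we were unable to assess whether they used MOP". Neither sentence names an outcome to which it is restricted.

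One sensitivity analysis addresses the no-fill group. Its purpose is "to assess the impact of those without CVD medication fills during follow-up", and its method is "including them in the analytic population as non-users of MOP at follow-up".

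PDC with an 80% cut-off appears only in the inclusion criteria. The documents do not define adherence at follow-up, and they do not give the follow-up length, the allocation ratio or the number of patients without a fill.

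**The concern.** An ITT comparison keeps every randomised patient in the assigned arm whatever happens next. Having a fill happens after randomisation, and the outreach could change it. It is also close to the outcome: PDC is built from fills, so a patient who fills nothing may be the plainest case of non-adherence.

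A comparison of fillers only can therefore mix a change in adherence with a change in who is counted. If the outreach brings in patients who would otherwise have filled nothing, and most of them stay below the adherence threshold, the intervention arm's percentage falls although nobody has done worse.

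The stated reason does not help, because not knowing whether a patient used MOP is no obstacle to classifying adherence. The sensitivity analysis has a broad stated purpose, but the only value it assigns is MOP non-use. A reader cannot tell whether any analysis puts these patients back for adherence, or with what value. What is at stake is how the Aim 2 result should be read.

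**Working it through.** The plan has no figure to reproduce: the sample size stands without a power calculation, an adherence rate or a no-fill share. What follows is an illustration.

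**Inputs**
- From the documents: 63,012 participants (STUDY POPULATION) and two arms (STUDY DESIGN).
- Assumed: 1:1 allocation, so 63,012 / 2 = 31,506 per arm; no deaths or disenrolments; fill proportion in usual care f = 0.90; adherent share of usual-care fillers a = 0.45; the outreach changes the fill proportion by d; a share q of the added fillers is adherent; everyone else is unchanged; no fill counts as non-adherent.

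**Formulas**
- Fillers-only difference = (fa + dq)/(f + d) - a = d(q - a)/(f + d)
- All-patient difference = dq
- Distortion = the first minus the second

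Example, d = 0.01 and q = 0.25: 0.01 × (0.25 - 0.45)/0.91 = -0.22 pp against 0.01 × 0.25 = +0.25 pp, a distortion of -0.47 pp.

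| Rise in filling (points) | q | Fillers-only (pp) | All-patient (pp) | Distortion (pp) |
|---|---|---|---|---|
| 0.2 | 0 | -0.10 | 0 | -0.10 |
| 0.2 | 0.5 | +0.01 | +0.10 | -0.09 |
| 0.5 | 0 | -0.25 | 0 | -0.25 |
| 0.5 | 0.5 | +0.03 | +0.25 | -0.22 |
| 1 | 0 | -0.49 | 0 | -0.49 |
| 1 | 0.25 | -0.22 | +0.25 | -0.47 |
| 1 | 0.5 | +0.05 | +0.50 | -0.45 |

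**Range.** With q = 0, no-fill shares of 5-20% and adherence of 30-60%, the fillers-only difference is -0.06 to -0.15 pp for a 0.2-point rise, -0.16 to -0.37 pp for 0.5 and -0.31 to -0.74 pp for 1.

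**Direction.** The sign follows the fill shift. If filling fell by 1 point and all who stopped filling were non-adherent, the result would be -0.01 × (-0.45)/0.89 = +0.51 pp against 0.

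**Equal no-fill shares.** With 10% no-fill in both arms and a 1.0-point difference among fillers, the all-patient difference is 0.90 × 1.0 = 0.90 points (0.95 at 5% no-fill, 0.80 at 20%). Equal shares remove the distortion only if adherence among fillers is also equal by arm.

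**Coding.** If a share r of no-fill patients counts as adherent, the all-patient difference is d(q - r). With d = 0.01, q = 0 and r = 0.25 it is -0.25 pp instead of 0, and the distortion shrinks from -0.49 to -0.24 pp.

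**Scale.** For d = 0.01 and q = 0, the standard error of the fillers-only difference is 0.416 pp, so the 95% half-width is 1.96 × 0.416 = 0.82 pp. A comparison of no-fill counts by arm would detect a shift of 0.2, 0.5 or 1 point with probability 13%, 56% or 99%.

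**The case against.** The strongest reply is that the no-fill exclusion was meant for MOP outcomes only, since the reason given is about MOP. That cannot be ruled out. But the wording sets no limit by outcome, and the no-fill group is added to exclusions from the analysis as a whole. If MOP only was meant, a sentence saying so is still needed, along with the adherence value these patients received. The same applies to the suggestion that re-inclusion in the sensitivity analysis extends to adherence: it may, but no value is stated.

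Second, the effect on filling may be slight. STUDY PROCEDURES says "The letter and email outreach will be delivered only once", with a recorded call added at the two KP sites. A 0.2-point rise distorts adherence by only about 0.1 pp, and a 1-point shift would almost surely show in counts by arm. This stands, and it argues for modest claims about bias.

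Third, no fill need not mean non-adherent: supply may have been carried over or a drug discontinued. This also stands, and it is why one coding is not enough.

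A reader might infer that the exclusion could produce a false claim of benefit. The documents do not support that. In the extreme 1-point case (q = 0), the rejection probability of about 22% against a nominal 5% splits into 0.220 against the intervention and 0.001 in its favour, where the nominal figure is 0.025 per side. A spurious benefit of this kind would need the outreach to reduce filling, which nothing in the documents suggests. Nor may a reader infer the opposite, that similar no-fill counts by arm make the exclusion harmless: beyond the arithmetic above, equal shares do not show that the same kinds of patients filled in each arm.

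**Conclusion.** The point holds as a defect of labelling and specification for Aim 2. As written, the adherence comparison is restricted to patients who stayed alive, stayed enrolled and had a fill. The ITT label does not fit that population, and no described analysis clearly gives no-fill patients an adherence value. That much rests on the text alone.

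A material bias is not established. Its size and direction depend on no-fill shares by arm, which the documents do not give. Under the assumed inputs, a 1-point rise in filling distorts the adherence difference by about -0.45 to -0.5 pp, smaller rises distort roughly in proportion, and the likely consequence is that a small benefit is hidden.

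A reader might also infer that the primary outcome is undermined. It is not on this ground: Aim 1 is MOP use, and the planned sensitivity analysis restores no-fill patients there with a stated value. The point should be fixed, but it does not put the trial's main result in doubt.

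**What to change.** 1. Describe the adherence comparison as limited to patients alive, enrolled and with a fill, and drop the ITT label for it; or state that the no-fill exclusion applies to MOP outcomes only.
2. State how adherence at follow-up is defined. Beside the described comparison, add an adherence analysis of all randomised patients who remain alive and enrolled, with no-fill patients counted as non-adherent (below the entry threshold of 80% PDC, if that is also the follow-up definition). Add an alternative coding for carried-over supply or a discontinued drug. Say that this analysis still omits deaths and disenrolments.
3. Report no-fill, death and disenrolment counts by arm.

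Leave the MOP sensitivity analysis unchanged.

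The cost is some wording and one added analysis on data already held. There are three drawbacks. DATA ANALYSIS says the KP sites were collapsed "based on the similarity of study results in the two sites", so results were apparently known and the added analysis would probably have to be labelled post hoc. Absolute adherence percentages fall with the no-fill share: 0.45 × 0.90 = 40.5% instead of 45% at 10% no-fill, or 0.60 × 0.80 = 48% instead of 60% at 20%. And under the main coding, some patients whose drug was stopped count as non-adherent in both arms.

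### The primary comparison of mail-order use is labelled intent-to-treat but drops patients with no CVD fill after randomisation, so its estimate is conditional on refilling

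*Combined protocol and SAP*

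**What the plan says.** Aim 1 (Objective) is to test whether outreach "will increase rates of mail order pharmacy use (Primary Outcome) in diabetes patients at high risk for poor health outcomes". The Data Analysis section compares MOP use, along with CVD medication adherence, "between the two arms using Chi-square tests in an intent-to-treat (ITT) analysis".

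The same section then makes two exclusions based on events after randomisation:
- "Patients who died or who disenrolled from their health plan during follow-up were excluded from the analysis".
- Patients without a CVD medication fill during follow-up "were also excluded since we were unable to assess whether they used MOP".

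A sensitivity analysis addresses the second exclusion "by including them in the analytic population as non-users of MOP at follow-up". Nothing comparable is described for the first.

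The documents do not define MOP use operationally: neither the drugs that count nor the follow-up window is stated. The nearest indications are the inclusion criterion "Have no evidence of mail order pharmacy use to refill oral CVD risk factor medications" and the related outcome in Data Analysis, the percentage of CVD drug fills delivered by mail. The population section gives "63,012 total participants", with no allocation ratio, expected MOP rate or no-fill share.

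**The concern.** Whether a patient fills a CVD drug during follow-up is decided after allocation. The outreach may influence it, because Aim 2 tests whether the same outreach improves adherence. Patients were also selected for poor adherence (PDC below 80% on at least one oral CVD drug), so the group without any fill need not be negligible.

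The reason given for dropping them does not suit a yes/no outcome. A patient who is still enrolled and has no recorded CVD fill has no recorded CVD fill by mail. The sensitivity analysis assigns exactly that status, so a status could be assigned.

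Aim 1 is not restricted to patients who keep refilling. The headline result would be read as the effect of sending the outreach to this population, whereas it describes uptake among those who refilled. If the outreach changes who refills, the two denominators are no longer formed by randomisation alone.

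**Working it through.** The plan states no figure on this point that could be reproduced. All rates and no-fill shares below are assumptions. Equal allocation is also assumed (63,012 / 2 = 31,506 per arm), and deaths and disenrolments are set aside.

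**Set-up.** Let p0 and p1 be MOP use among all enrolled patients in usual care and intervention, and f0 and f1 the shares with no CVD fill. No-fill patients contribute no users, so the rate among refillers is p / (1 − f) in each arm.

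**Equal shares (f0 = f1 = f).** The risk ratio is unchanged and the risk difference is multiplied by 1 / (1 − f):
- f = 5%: 1 / 0.95 = 1.053
- f = 10%: 1 / 0.90 = 1.111
- f = 20%: 1 / 0.80 = 1.250

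For example, 10% v 12% (2.0 points) is reported as 2.1, 2.2 or 2.5 points.

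**Unequal shares, no true effect.** The risk ratio is multiplied by (1 − f0) / (1 − f1).
- *Small gap.* With p = 8.5% in both arms and f0 = 15%, usual care shows 8.5 / 0.85 = 10.00%. With f1 = 14% the intervention arm shows 8.5 / 0.86 = 9.88% (−0.12 points); with f1 = 16% it shows 8.5 / 0.84 = 10.12% (+0.12 points). Refillers per arm are about 0.85 × 31,506 = 26,780, so the standard error is √(2 × 0.10 × 0.90 / 26,780) = 0.26 points. The shift is under half a standard error.
- *Larger gap.* With p = 10% and f0 = 20%, f1 = 18% gives a ratio of 0.80 / 0.82 = 0.976, and f1 = 22% gives 0.80 / 0.78 = 1.026. At a two-sided 5% level, the chance of a false significant result in that direction is about 18% and 19%, against a nominal 2.5%. It is about 11% if p = 5%, and 36% to 38% if p = 20%.

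**Unequal shares, true effect 10% v 11%** (1.00 point, ratio 1.100), f0 = 20%. Usual care shows 0.10 / 0.80 = 12.50%.

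| f1 | Intervention rate among refillers | Difference (points) | Risk ratio |
|---|---|---|---|
| 22% | 0.11 / 0.78 = 14.10% | 1.60 | 1.128 |
| 18% | 0.11 / 0.82 = 13.41% | 0.91 | 1.073 |
| 16% | 0.11 / 0.84 = 13.10% | 0.60 | 1.048 |

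The absolute gain is overstated when p1·f1 / (1 − f1) exceeds p0·f0 / (1 − f0). Here that means f1 / (1 − f1) above 0.10 × 0.25 / 0.11 = 0.227, or f1 above 0.227 / 1.227 = 18.5%. Below that, the gain is understated.

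**The case against.** The strongest reply is that nothing is hidden. The section states the exclusion and its reason, and then reports the analysis that a critic would want. What remains is a dispute over which of two disclosed analyses is the main one. That limits the seriousness of the point, but a sensitivity analysis does not correct a main estimate that carries the wrong label.

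The bias may also be small. Letter and email were sent once, and a one-point gap in no-fill shares moves the result by 0.12 points in the example. With equal shares the risk ratio, which is the measure used for race/ethnicity, does not change. This stands as to size. The documents neither support nor exclude a larger gap.

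The exclusion is understandable for the percentage of CVD fills delivered by mail, because a patient without fills has a zero denominator. That stands too, and the point here is confined to the yes/no outcome.

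Finally, treating a no-fill patient as a non-user is an inference. It depends on MOP use meaning mail delivery of CVD drugs and on fills being captured in the data. The inclusion criterion and the percentage-of-fills outcome point to that meaning, but the documents do not state it, and they do not describe completeness of capture across the three sites. The condition has to be stated with the point.

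**Conclusion.** The point holds, on the condition that MOP use means mail delivery of CVD drugs. The main analysis of the primary outcome conditions on a post-randomisation event, and the stated reason does not justify this for a yes/no outcome. The size in this trial cannot be computed from the documents; the ranges above rest on assumed rates and shares.

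Three stronger readings are not supported:
- A reader might take the sensitivity analysis for an analysis of all randomised patients. It restores only the no-fill patients. As far as the text says, deaths and disenrolments remain excluded, so no analysis of all 63,012 is described.
- A reader might infer that the exclusion always exaggerates the gain. Uptake within each arm is higher among refillers whenever some patients have no fill, but the difference between arms is sure to be inflated only when the shares are equal and the effect is positive. With no-fill shares of 20% v 18%, a true 1.00-point gain appears as 0.91.
- A reader might infer that the dropped patients are those for whom outreach failed. The documents give no reasons for not filling, and usual-care patients received no outreach.

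**What to change.** In Data Analysis:
- Make the analysis that counts no-fill patients as non-users the primary analysis of MOP use, overall and by site and race/ethnicity.
- Relabel the present analysis as secondary, for example *MOP use among patients who refilled*.
- Report the number of no-fill patients by arm.
- Define MOP use as mail delivery of CVD drugs, if that is what is meant.
- State that deaths and disenrolments remain excluded, if so, and do not describe the result as including all randomised patients.

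The cost is low. The overall analysis is described as already done. The text says all analyses were stratified by site, but it does not say that the sensitivity analysis was repeated by race/ethnicity, so some stratified versions may need rerunning. Reported uptake will be somewhat smaller. The document describes its analyses in the past tense; if results are already known, the change should be disclosed as made after the fact and both analyses shown.
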